## 2. PROTOCOL SUMMARY FOR STUDY RVT-1401-2002

Study Title	A Phase 2a, Multicenter, Randomized, Double-Blind, Placebo-Controlled Study with an Open-Label Extension of RVT-1401 in Myasthenia Gravis Patients
Objectives	
Primary
 
To assess the safety and tolerability of RVT-1401 in AChR antibody positive MG patients over a 6-week treatment period
 
To examine the effects of RVT-1401 on total IgG, IgG subclasses (1-4) and anti-AChR-IgG levels
 
Secondary
 
To examine RVT-1401 PK following repeat doses in patients with Myasthenia Gravis (MG)
 
To measure anti-RVT-1401 antibodies following repeat doses in patients with MG and assess any potential impact on PK or PD
 
To examine the effects of RVT-1401 on the Quantitative Myasthenia Gravis (QMG) score
 
To examine the effects of RVT-1401 on the proportion of patients with improvement on the QMG score by <math>\geq 3</math> points from baseline
 
To examine the effects of RVT-1401 on Myasthenia Gravis-Activities of Daily Living score (MG-ADL)
 
To examine the effects of RVT-1401 on the proportion of participants with an improvement on the MG-ADL Score by <math>\geq 2</math> points
 
To examine the effects of RVT-1401 on the Myasthenia Gravis Composite (MGC) score
 
To examine the effects of RVT-1401 on the proportion of participants with an improvement on the MGC Score by <math>\geq 3</math>
 
To examine the effects of RVT-1401 on the Myasthenia Gravis Quality of Life (MG-QOL15r) score
 
Open-Label Extension Objective:
 
The objective of the OLE is to evaluate the effect of switching to every 2-week dosing regimen of 340 mg RVT-1401 on all study endpoints.

Study Phase	Phase 2a
Target Population	Myasthenia Gravis
Number of Participants Planned	Approximately 21
Number of Study Centers Planned	Approximately 10-15
Study Design	Phase 2a, randomized, double-blind, placebo-controlled study, with an open-label extension (OLE) to investigate the safety, tolerability, PK, PD, and efficacy of two dosing regimens of RVT-1401
Duration of Treatment	6 weeks or 12 weeks (3 additional doses for the OLE)
Criteria for Evaluation (Endpoints)	
Primary
 
Assessment of safety and tolerability by analysis of adverse events (AEs) data and changes from baseline in vital signs, clinical laboratory values, and electrocardiograms
 
Change from baseline in levels of total IgG and IgG subclasses (1-4)
 
Change from baseline in levels of anti-AChR-IgG
 
Secondary
 
PK Parameters of AUC (0-168 h) and maximum concentration (Cmax) after first and last dose
 
Concentration of RVT-1401 pre-dose (Ctrough)
 
Immunogenicity determined by change from pre-dose in anti-RVT-1401 antibodies, characterization of any anti-RVT-1401 to confirm neutralization potential
 
Change from baseline in the QMG Score
 
Proportion of participants with an improvement on the QMG score by <math>\geq 3</math> points from baseline
 
Change from baseline in the MG-ADL score
 
Proportion of participants with an improvement on the MG-ADL Score by <math>\geq 2</math> points
 
Change from baseline in the MGC score
 
Proportion of participants with an improvement on the MGC

	Score by $\geq 3$ points
	Change from baseline in the MG-QOL15r score

### 3. INTRODUCTION

#### 3.1. Background

RVT-1401 is a fully human anti-neonatal Fc receptor (FcRn) monoclonal antibody. FcRn is critical to the regulation of Immunoglobulin G (IgG) [Roopenian, 2007 ]. In addition to its central role in mediating the transport of IgG within and across cells of diverse origin, it also serves to rescue IgG from degradation, thereby prolonging its circulating half-life [Roopenian, 2007]. Targeting the FcRn pathway has been shown to dramatically reduce circulating IgG, thus supporting its use in the treatment of auto-Ab mediated autoimmune diseases.

##### 3.1.1. Myasthenia Gravis

Myasthenia Gravis (MG) is a chronic autoimmune neuromuscular disease that causes weakness and fatigue. The muscles that control eye and eyelid movement are particularly susceptible to weakness, but other muscles for chewing, talking, and swallowing are frequently involved. Patients with ocular MG often progress to more severe, generalized disease with involvement of bulbar, axial, limb, and/or respiratory muscles.

MG is part of a spectrum of autoimmune diseases in which pathogenic IgG (pIgG) is thought to directly cause and/or exacerbate the condition. MG results from binding of autoantibodies to proteins that lead to impaired transmission at the neuromuscular junction. Most commonly, in approximately 80% of MG patients, anti-acetylcholine receptor (AChR) IgG is detected, and in a smaller subset (approximately 40-50% of patients who are seronegative for anti-AChR IgG), anti-muscle-specific kinase receptor (MuSK) IgG is detected [Gilhus, 2015]. Recently, autoantibodies against low-density lipoprotein related receptor protein 4 (Lrp4) have been described in seronegative MG patients with varying frequencies ranging from 2 to 50% [Higuchi, 2011; Zisimopoulou, 2014; Zhang, 2012; Pevzne, 2012]. The clinical characteristics of Lrp4-MG have yet to be fully characterized [Evoli, 2015].

The chronic nature of MG requires patients to cope with fluctuating symptoms and often maintain treatment with acetylcholinesterase inhibitors, corticosteroids, immunosuppressants, plasmapheresis, and/or intravenous immunoglobulin [Sanders, 2016; Nowak, 2018]. Despite chronic treatment, up to 20% of MG patients can progress into myasthenic crisis [Utsugisawa, 2014]. MG has widespread and significant negative effects on quality of life including daily activities such as eating, walking, and speaking [Nowak, 2018]. Overall, the persistent muscle weakness associated with MG often negatively interferes with patients' ability to engage in daily activities, including demands of work, family, social functions, and physical activities [Paul, 2001].

Current treatment guidelines recommend pyridostigmine as first line therapy with or without concomitant corticosteroids for patients who are anti-AChR-IgG-positive [Sanders, 2016]. If corticosteroids are contraindicated, nonsteroidal immunosuppressive (IS) agents are used, including azathioprine (AZA), cyclosporine, mycophenolate mofetil, methotrexate, and tacrolimus. Despite existing treatment regimens, current methods provide variable efficacy. Failure rates for current treatments range from 15–53%

depending upon the presentation and diagnosis, and up to 20% of patients treated with IS agents experience severe side effects [Sanders, 2010]. Thus, there is a need for more efficacious and safer therapies.

## 3.2. Rationale

### 3.2.1. Study Rationale

RVT-1401 functions by inhibiting the binding of IgG to FcRn. This results in the rapid catabolism of IgG via lysosomal degradation. In MG, RVT-1401 treatment is expected to lead to a significant reduction in the levels of pIgG such as anti-AChR-IgG, anti-MuSK-IgG, and anti-Lrp4-IgG that have been identified to drive disease pathology. While this initial Ph2a study will focus on anti-AChR IgG positive patients to reduce heterogeneity, future studies may also assess the efficacy of anti-FcRn blockade in seronegative patients.

The purpose of the current study is to confirm safety/tolerability and key pharmacodynamic (PD) effects that are considered to drive clinical benefit (reduction of total IgG and anti-AChR-IgG) in MG patients. A positive correlation between total and pIgG reduction and clinical improvement in MG patients has been previously observed with another anti-FcRn treatment (ARGX-113). A 6-week open-label extension (OLE) has been included to assess transition from weekly dosing regimens for RVT-1401 and placebo to a every 2-week dosing regimen (3 additional doses of 340 mg). Results from this trial will be used to support progression into a larger and longer study designed to confirm clinical efficacy.

### 3.2.2. Dose rationale

In MG, RVT-1401 treatment is expected to lead to a significant reduction in the levels of pIgG such as anti-AChR-IgG and anti-MuSK-IgG that are considered to be a primary driver of disease pathology. Available evidence suggests that reducing the levels of pIgG in MG is associated with clinical benefit. For example, the use of IVIG treatment has been shown to reduce AChR autoantibodies by ~30% from baseline and this is associated with clinical improvement [Liu, 2010]. Recently, data with another anti-FcRn compound (ARGX-113, efgartigimod), reported clinical improvement on the Quantitative Myasthenia Gravis (QMG) and Myasthenia Gravis-Activities of Daily Living (MG-ADL) scores with an approximate 80% reduction in total IgG and 50% reduction in AChR-IgG after once weekly administration for 4 weeks [Howard, 2018]. These data provide a target range for potentially therapeutic PD effects; however it is unknown whether there is a minimum threshold for pIgG reduction that translates into clinical efficacy.

RVT-1401 is designed to provide patients with a treatment option that allows home administration via subcutaneous (SC) injection. This significantly reduces the burden that an IV infusion treatment (e.g., IVIG, Soliris® and other anti-FcRn treatments in development) places on patients who will be required to go to an infusion center to receive their treatment.

Two dosing regimens of RVT-1401 will be assessed in double-blind phase of this study. Both will involve once weekly SC injections:

- Dosing Regimen A -680 mg weekly for 6 weeks, and
- Dosing Regimen B - 340 mg weekly for 6 weeks

Given that there is a practical limit on the volume that can be administered via SC injection, these two doses represent what can be administered as a single SC injection (340 mg) and two SC injections (680 mg) per week with the current formulation.

The OLE will involve 1 dosing regimen as a single SC injection:

- 340 mg every 2 weeks for 6 weeks

The OLE dose of 340 mg every 2 weeks will allow for the exploration of the effect of less frequent dosing of RVT-1401. This dose comprises a less frequent regimen with a convenient single SC injection. Since the frequency of dosing will decrease, the drug exposure over the dosing interval for subjects who were on active drug will decrease by approximately 8- 10 -fold for Regimen A and by 1-2 fold for Regimen B.

### **Expected Treatment Effect**

[figure not shown]
The proposed dosing regimens are expected to provide a sustained total IgG reduction of approximately 75-80% and 65-70% for Regimen A and B respectively, following the fourth or fifth dose. It is expected that the nadir IgG reduction will occur by the 5th dose and be maintained following the sixth dose before rising back to baseline over the next 6 to 8 weeks. These assumptions are supported by preliminary PD results, shown in Figure 1, from the ongoing Phase 1 clinical study RVT-1401-1001 (Section 3.2.3). In healthy participants, 4 weekly SC injections of 680 mg of RVT-1401 produced an average total IgG percent reduction from baseline of 78%.

For participants that enter into the OLE, IgG levels will rise over the 2-week interval between week 6 and the start of OLE dosing at week 8. The IgG levels are expected to oscillate between decreasing and increasing over the next 3 doses, with trough IgG levels expected to rise by 15-25% above the nadir levels achieved during the treatment phase in the double-blind part of the study. Subjects who switch to 340 mg every 2 weeks from the placebo treatment are expected to achieve an IgG reduction of approximately 35-45% after the last OLE dose. Upon completion of OLE dosing, all subject IgG levels are expected to return to baseline over the next 6-8 weeks.

In study RVT-1401-1001, the inter-individual variability in IgG reduction and PK was larger in the 340 mg cohort vs. the 680 mg cohort; this difference can be explained by lower receptor occupancy in the 340 mg cohort throughout the dosing interval across all individuals. It is also noteworthy that, with both doses, the variability in exposure decreased with repeat dosing. This may indicate that full receptor occupancy is not lost within the dosing interval, and that with subsequent doses, more receptors are being occupied or remain occupied.

In the repeat dose 340 mg cohort, there were some individuals who did not achieve nadir IgG concentration until after the last dose, indicating they may have not reached steady state. In contrast, most subjects in the 680 mg cohort achieved nadir concentration prior to the last dose and maintained that response until after the last dose, indicating steady state response was achieved. Data from this study will be used to support dose selection in future studies.

**Figure 1: Mean(+/-SD) Serum IgG Reduction Following Multiple SC Doses of RVT-1401**

### 3.2.3. Clinical Experience

RVT-1401 has been studied in two Phase 1 clinical studies (HL161BKN-001 and RVT-1401-1001) designed to assess the safety, tolerability, PK, and PD following single (intravenous [IV] and SC) and multiple (SC) doses in healthy participants. As of December 14, 2018 RVT-1401 has been administered to 65 healthy participants at the following doses: 0.1 mg/kg as a 1-hour intravenous (IV) infusion (n=4), 100 mg as a 1-hour IV infusion (n=6), 340 mg as a 1-hour IV infusion (n=6), 0.5 mg/kg SC injection (n=3), 1.5 mg/kg SC injection (n=6), 5 mg/kg SC (n=6), 340 mg SC injection (n=6), 500 mg SC injection (n=6), 765 mg SC injection (n=6). Eight participants have received repeated 340 mg SC injections weekly for 4 weeks and 8 participants have received repeated 680 mg SC injections weekly for 4 weeks.

### **3.2.3.1. Safety**

See Investigator's Brochure for Details.

RVT-1401 has been well tolerated with no Grade 3 or 4 adverse events (AEs), and no withdrawals due to AEs. There was one SAE (Malpighian carcinoma in left side of the neck) considered unrelated to study drug.

All AEs in subjects receiving RVT-1401 have been reported as mild or moderate. One subject who received placebo experienced severe (Grade 3) pain from urinary lithiasis.

The most frequent AE for both groups was injection site reactions (erythema/ and or swelling). Overall, injection site reactions have resolved within a few hours after dosing; there were two exceptions of mild swelling (one RVT-1401 and one placebo subject) that resolved after 3 and 4 days, respectively. The frequency of injection site reactions was not dose-related and similar reactions were observed with placebo. Additionally, injection site reactions were not consistently observed following every injection in the repeat dose cohorts.

Preliminary data suggest no subject who has received RVT-1401 had clinically relevant changes in laboratory findings, electrocardiograms (ECGs), or vital signs.

### **3.2.3.2. Pharmacokinetics**

RVT-1401 exhibited non-linear pharmacokinetics (PK) following single SC administration across doses ranging from 0.5 mg/kg to 765 mg. The non-linearity is consistent with RVT-1401 exhibiting target mediated disposition PK. In addition to single dose administration, RVT-1401 has also been administered weekly SC for 4 weeks at doses of 340 and 680 mg. The observed mean concentration-time profile following the first and last dose were generally similar, rising to peak concentration between 2 and 3 days after the dose and then declining beginning 4 days after administration up until the next dose. The rate of elimination was more rapid following administration of 340 mg compared to 680 mg, indicative of target mediated drug disposition. Across both dosing cohorts there was accumulation in the exposure measures of Cmax and AUC(0-168). The accumulation in Cmax and AUC(0-168) in the 340 mg cohort was 7 and 8.7-fold respectively between the first and last dose, and 2.23 and 2.64, respectively in the 680 mg cohort. There was large variability in Cmax and AUC(0-168) after the first dose of 340 mg, whereas there was less variability following first SC dose of 680 mg, consistent with what was observed in single dose data. Overall there was reduction in the inter-individual variability around Cmax and AUC(0-168) after subsequent doses. Following the last dose in the 680 mg cohort, the profile shows characteristics of target mediated drug disposition, with a linear elimination phase from ~96 hours to 168 hours after the last dose, at which time the elimination was very rapid from 168 hours to 336 hours post dose. Exposures increased more than dose proportionally when comparing week four of the 340 mg dose to exposures following the 680 mg SC dose.

### 3.2.3.3. Pharmacodynamic

Following the administration of single SC doses of RVT-1401, total IgG reduction increased with increasing dose, with a maximum reduction of 47% observed after a fixed dose of 765 mg. The nadir for IgG reduction following single SC dosing occurred between days 8-15 in most individuals. IgG serum levels on average returned to within 90% of baseline by 43 days after drug administration. Albumin levels were also reduced from baseline when compared to placebo showing a similar dose related trend. The highest reduction occurring following the 765 mg SC dose (average ~14.5%) but were not considered to be clinically significant reductions as all patients remained within normal limits (3.5 g/dL to 5.5 g/dL) and levels recovered quickly, returning to baseline ~ 2 weeks after nadir.

The amount of IgG reduction has also been assessed following weekly SC administration of 340 and 680 mg of RVT-1401 or placebo for 4 weeks. There were 8 subjects with data out to day 35, that were included in a preliminary PD analysis for the 680 mg cohort and 7 subjects with data out to day 49 that were included in the analysis for the 340 mg cohort. One subject only received 2 doses of 340 mg prior to withdrawing due to personal reasons, their data was not included in the preliminary PD analysis. There were 4 placebo subjects with data out to day 35 pooled across two cohorts for analysis of PD endpoints. Figure 1 presents the mean IgG concentration-time profiles for both weekly SC administration of 340 mg and 680 mg doses. Figure 1 shows a reduction in serum IgG as a percent of pre-dose across both 340 mg and 680 mg cohorts. In contrast, the placebo group demonstrated minimal changes in serum IgG as a percent of pre-dose. The reduction in serum IgG was more rapid following the 680 mg SC compared vs 340 mg SC. The median IgG nadir concentration occurred prior to the last dose in the 680 mg cohort whereas for 340 mg, it occurred approximately 3 days after the last dose. The finding that the 680 mg cohort achieved nadir concentration following the 3rd dose and maintained serum IgG reduction after the 4th dose, indicates a maximum response has likely been achieved, and that higher doses or more frequent dosing would yield little additional benefit. This is consistent with data from other anti-FcRn agents in development that have observed a maximum percent reduction in serum IgG from baseline of ~ 75-80%.

Preliminary data following the last dose across both cohorts shows that IgG levels were within normal range and within 30% of the baseline value by 5 weeks after the last dose (average (SD) IgG concentration was 8.64 (2.73) g/L, and 8.95 (2.03) g/L for the 340 mg and 680 mg cohorts, respectively). The return towards baseline indicates the effect is reversible.

The change in serum albumin was also assessed following repeat SC administration of 340 and 680 mg of RVT-1401 as compared to pooled placebo. Following both single and repeat dosing RVT-1401 serum albumin concentrations were reduced in a dose dependent fashion, whereas placebo subjects showed little to no change in albumin concentrations. While there was a reduction in albumin concentrations following weekly dosing of 340 mg of RVT-1401, individual concentrations remained within normal limits (>3.5 g/dL) for serum albumin. Following weekly administration of 680 mg of RVT-1401, all but 1 individual remained above 3.0 g/dL for the duration of dosing and most

individuals had nadir albumin concentration prior to last dose, indicating that maximum albumin reduction had been achieved. In all individuals, albumin levels were within normal limits (>3.5 g/dL) within 3-4 weeks of the last dose for the 680 mg cohort. Across both cohorts, on average, individuals were within 95% of their baseline concentration 5 weeks after the last dose, indicating the reversibility of the effect of RVT-1401 on albumin. There were no clinical signs or symptoms reported with these transient albumin reductions.

Additional information is available in the current Investigator's Brochure (IB).

### 3.3. Benefit: Risk Assessment

Summaries of findings from both clinical and non-clinical studies conducted with RVT-1401 can be found in the current IB.

#### 3.3.1. Risk Assessment

Potential Risk of Clinical Significance	Mitigation Strategy	
	Impact on Eligibility	Monitoring and Stopping Criteria OR Management Criteria
The potential for allergic reactions exists following administration of any protein to human participants.	Participants with history of significant allergic reactions are ineligible.	Participants will be closely monitored for reactions for up to 1 hr post-dose before they leave the clinic. If during the course of study drug administration, the participant experiences a drug related AE of Grade 3 (severe) or greater severity, study drug administration will be stopped.
Changes in circulating complement	None	Serum complement will be monitored throughout the study (Section 8.1). Abnormal values will be discussed with the study medical monitor.
Sustained hypogammaglobulinemia	The following participants will be ineligible: -Participants with a total IgG level of <6g/L at screening -Participant has had their spleen removed. -Participant has a past medical history of primary immunodeficiency, T-cell or humoral, including common variable immunodeficiency. -History of or known infection with human	Total IgG levels will be monitored throughout the study (Section 8.1) by an unblinded Medical Monitor. Transient depletion of IgG following administration of certain drugs (e.g., corticosteroids) are not generally associated with an increased risk of infections [Furst, 2008]. Furthermore, available data from other FcRn antagonists in development have not reported an increased risk of infection in short-term trials similar to RVT-1401-

	immunodeficiency virus (HIV), hepatitis B virus (HBV), hepatitis C virus (HCV), or Mycobacterium tuberculosis. Participants must have negative test results for HBV surface antigen, HBV core antibody, HCV antibody, HIV 1 and 2 antibodies, and a negative QuantiFERON®- tuberculin (TB) Gold test at Screening. Participants with an indeterminate QuantiFERON®-TB Gold test result will be allowed one retest; if not negative on retesting, the participant will be excluded. -Absolute neutrophil count <1500 cells/mm3	2002.
Sustained hypoalbuminemia	Investigator discretion	Serum albumin levels will be monitored throughout the study (Section 8.1) by an unblinded Medical Monitor. Treatment of hypoalbuminemia will be left to the discretion of the investigator and decision on dosing discussed with the study medical monitor.

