## **6.9. Stopping Criteria for Individual Participants**

### **6.9.1. Liver Chemistry Stopping Criteria**

Hepatic enzymes will be monitored in accordance with FDA drug-induced liver injury guidelines [FDA, 2009].

If the following liver test abnormalities develop, Study Treatment should be withheld immediately with appropriate clinical follow-up (including repeat laboratory tests, until a participant's laboratory profile has returned to normal/baseline status), and the event reported as a SAE:

- Alanine aminotransferase (ALT) or aspartate aminotransferase (AST)> 8 x upper limit of normal (ULN); or
- ALT or AST > 5 x ULN and persists for more than 2 weeks; or
- ALT or AST > 3 x ULN and total bilirubin > 2 x ULN or international normalized ratio (INR) > 1.5

- ALT or AST  $> 3 \times$  ULN with appearance of fatigue, nausea, vomiting, right upper quadrant pain or tenderness, fever, rash and/or eosinophilia ( $> 5\%$ ).

Rechallenge may be considered if an alternative cause for the abnormal liver tests (ALT, AST, total bilirubin) is discovered and the laboratory abnormalities resolve to normal or baseline values. The Investigator and sponsor must discuss and agree with any decision to rechallenge.

Rechallenge should not occur when the etiology of the liver test abnormalities is considered possibly drug induced.

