## 7.3. Blinding

This will be a double-blind study. The investigator and study site will also remain blinded to the IgG, albumin, total protein, alkaline phosphatase (ALP), and anti-AChR antibody data post screening as this could potentially unblind them. An unblinded Medical Monitor will review this lab data on an ongoing basis for safety. In order to maintain the blind of which treatment subjects received during the double-blind phase of the study, these labs will continue to be blinded to the investigator and study site in the OLE.

The following will apply throughout the study:

- The Investigator or treating physician may unblind a participant's treatment assignment **only in the case of an emergency** OR in the event of a serious medical condition when knowledge of the study treatment is essential for the appropriate clinical management or welfare of the participant as judged by the Investigator. Emergency unblinding will be available via the IWRS or via the unblinded pharmacist.
- The Investigator should make every effort to first contact the Medical Monitor or appropriate study personnel to discuss options **before** unblinding the participant's treatment assignment.
- If the Medical Monitor is not contacted before the unblinding, the Investigator must notify the Sponsor as soon as possible after unblinding.
- The date and reason for the unblinding (the event or condition which led to the unblinding) must be fully documented in the eCRF

A participant will be withdrawn if the participant's treatment code is unblinded by the Investigator or treating physician.

The Sponsor or their designee may unblind the treatment assignment for any participant with a SAE. If the SAE requires that an expedited regulatory report be sent to one or more regulatory agencies, a copy of the report, identifying the participant's treatment assignment, may be sent to Investigator in accordance with local regulations.

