## 8.2. Time and Events Table (With OLE and 6-week follow-up)

	Screening 	Treatment Period Week 1 (Days)			Treatment Period Weekly Visit (Weeks)				Treatment Period Week 6 (Days)			OLE and Follow-up Period Weekly Visit (Weeks)							Early Withdrawal Visit	
		Day 1 (Baseline)	Day 3	Day 5	2 (Day 8)	3 (Day 15)	4 (Day 22)	5 (Day 29)	6 (Day 36)	Day 38	Day 40	7	8	9	10	12	14	16	18	
Study Timepoint (Weeks)	Within 21 Days																			
Time Window (days)			+1 day	+1 day	+/-1 day	+/-1 day	+/-1 day	+/-1 day	+/-1 day	+1 day	+1 day	+1 day	+/-2 days	+/-2 days	+/-2 days	+/-2 days	+/-2 days	+/-2 days	+/-2 days	
Informed consent	X 	→	→	→	→	→	→	→	→	→	→	→	→	→	→	→	→	→	→	
Inclusion/exclusion criteria	X	X													X 					
Demographics and medical history	X																			
Height	X																			
Body weight	X	X																		
Complete physical examination	X	X																		
Brief physical examination																			X	
Vital signs 	X	X	X	X	X	X	X	X	X	X	X	X	X	X	X	X	X	X	X	
12-lead Electrocardiogram 	X	X			X		X		X										X	
Pregnancy test  (females)	X	X			X	X	X	X					X		X	X			X	
QuantiFERON®-TB Gold	X																			
Viral Serology	X																			
Urinalysis 	X	X			X	X	X	X				X							X	
Blood chemistry and hematology 	X	X			X	X	X	X				X							X	
Serum complement (CH50, C3) 		X			X	X	X	X				X							X	

	Screening 	Treatment Period Week 1 (Days)			Treatment Period Weekly Visit (Weeks)			Treatment Period Week 6 (Days)			OLE and Follow-up Period Weekly Visit (Weeks)								Early Withdrawal Visit		
		Day 1 (Baseline)	Day 3	Day 5	2 (Day 8)	3 (Day 15)	4 (Day 22)	5 (Day 29)	6 (Day 36)	Day 38	Day 40	7	8	9	10	12	14	16	18		
Study Timepoint (Weeks)	Within 21 Days																				
Time Window (days)			+1 day	+1 day	+/-1 day	+/-1 day	+/-1 day	+/-1 day	+/-1 day	+1 day	+1 day	+/-2 days									
Immunoglobulins (IgM, IgA) 		X				X			X			X	X	X						X	X
RVT-1401 PK sampling 		X	X	X	X	X	X	X	X	X	X	X	X	X	X	X	X	X		X	
Total IgG 	X	X	X	X	X	X	X	X	X	X	X	X	X	X	X	X	X	X	X	X	
Immunoglobins (IgG subclasses) 		X	X	X	X	X	X	X	X	X	X				X						
Anti-RVT- 1401 antibody 			X			X						X				X			X	X	
Nab Assessment 			X			X						X				X			X	X	
anti-AChR antibody 	X	X	X	X	X	X	X	X	X	X	X	X	X	X	X	X	X	X	X	X	
Drug administration			X			X	X	X	X	X			X		X	X					

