#### **Clinical Chemistry**

Blood urea nitrogen (BUN)	Potassium	AST (SGOT)	Total and direct bilirubin
Creatinine	Chloride	ALT (SGPT)	Uric Acid
Glucose fasting [on Day 1 (baseline) and Week 7 only]	Total carbon dioxide (CO 2 )	Gamma glutamyltransferase (GGT)	Albumin
Sodium	Calcium (corrected)	Alkaline phosphatase (ALP)	Total Protein
Serum complement (CH50, C3)	Immunoglobulin M (IgM)	Immunoglobulin A (IgA)	
Immunoglobulin G (IgG)			

Since changes in ALP, total protein and albumin level can potentially unblind the investigator to which dose the participant has been randomized to; values for ALP, total protein, and albumin levels will be blinded to the site. An unblinded Medical Monitor will review this lab data on an ongoing basis for safety.

NOTE: Details of Liver Chemistry Stopping Criteria and Follow-Up Procedures are given in Appendix 2: Liver Safety Required Actions and Follow up Assessments.

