### **10.3.3. Safety Analyses**

Safety will be evaluated by assessment of clinical laboratory tests, physical examinations, vital signs measurements, and ECG readings at various time points during the study, and by the documentation of AEs.

AE verbatim text will be coded and classified by body system and preferred (coded) term using the MedDRA. All AEs, both serious and non-serious will be listed. AE summaries by study part and treatment group, of the number and percent of participants reporting each event at least once will be generated.

Clinical chemistry, hematology, and urinalysis values will be listed for each participant and flagged high or low relative to the normal range where appropriate. Descriptive summary statistics will be created by study part, treatment and assessment time.

Other safety data will be summarized descriptively by treatment and time. Details will be provided in the SAP.

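### As read, the OLE schedule has no chemistry or complement draw between Week 7 and Week 18, so none at the three OLE dosing visits

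*Protocol*

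**What the plan says.** - **Monitoring commitments.** Protocol 3.3.1 says of complement: "Serum complement will be monitored throughout the study (Section 8.1". Of albumin it says: "Serum albumin levels will be monitored throughout the study (Section 8.1) by an unblinded Medical Monitor". Both point to 8.1, the schedule without the OLE. The section never cites 8.2.
- **Liver rules.** Protocol 6.9.1 says: "Hepatic enzymes will be monitored in accordance with FDA drug-induced liver injury guidelines". It gives no interval. One stopping limb depends on repeat values: "ALT or AST > 5 x ULN and persists for more than 2 weeks".
- **Timing.** Protocol 8 makes Tables 8.1 and 8.2 the authority on when each assessment is done. Protocol 5.1 starts OLE dosing at Week 8, with three doses 2 weeks apart, hence Weeks 8, 10 and 12.
- **The OLE table.** In 8.2, the row "Blood chemistry and hematology" (which carries liver enzymes and albumin) and the complement row are marked at Week 7 and then at Week 18, with no mark between.
- **Reporting.** Protocol 10.3.3 says of laboratory values: "Descriptive summary statistics will be created by study part, treatment and assessment time". Protocol 4 sets the OLE objective as the effect of the regimen switch on all study endpoints. Change in laboratory values is among the primary ones.

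**The concern.** The OLE is where the placebo arm first meets the drug, and where the active arms go from six doses to nine. If 8.2 is as read, no scheduled liver, albumin or complement value exists from a week before the first OLE dose until six weeks after the last.

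Three things would follow. The liver stopping rules would have no scheduled value to trigger them while OLE drug is being given. The unblinded Medical Monitor would have no scheduled albumin, ALP or total protein to review in that time. For participants who stay to the end, the OLE laboratory summary would rest on one post-dose visit, well off drug, so it could not describe laboratory changes on the every-2-week regimen.

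**Working it through.** The plan states no figure to reproduce. The check is a reading of the schedule rows followed by date arithmetic.

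**Step 1: the rows.** Each row below has the full 20 columns (Screening; Days 1, 3, 5; Weeks 2-6; Days 38, 40; Weeks 7-10, 12, 14, 16, 18; Early Withdrawal).

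| Row | Marks after Day 1, as read |
|---|---|
| 8.2 chemistry/hematology | Weeks 2-5, 7, 18 |
| 8.2 complement | Weeks 2-5, 7, 18 |
| 8.2 pregnancy test | Weeks 2-5, 8, 10, 12, 18 |
| 8.1 chemistry/hematology | Weeks 2-6, Day 40, Week 18, Early Withdrawal |
| 8.1 complement | Weeks 2-6, Day 40, Week 18, Early Withdrawal |

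Chemistry and complement have 0 marks at the 3 OLE dosing visits. The pregnancy-test row in the same block has 3 of 3, so those columns did carry marks through the reading.

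**Step 2: could a column shift explain it?** Between the Weeks 2-5 block and the last mark, each 8.2 row holds a single mark. A shift could therefore cover at most one OLE visit. Protocol 8.4.4 places that mark at Week 7, because it lists "Glucose fasting [on Day 1 (baseline) and Week 7 only". A shift does not close the gap; only lost marks would. Table 8.1 also has nothing from Week 8 to Week 16, but no drug is given there in that time.

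**Step 3: dates.** Nominal day of Week n = 7(n - 1) + 1, which agrees with the table headings (Week 2 = Day 8, Week 6 = Day 36). So Week 7 = 43, Week 8 = 50, Week 10 = 64, Week 12 = 78, Week 14 = 92 and Week 18 = 120.

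- Gap between draws: 120 - 43 = 77 days. If each end may move by 2 days, it is 73 to 81. If the Week 7 mark is really Day 40, as 8.1 reads, it is 120 - 40 = 80.
- First OLE dose to Week 18: 120 - 50 = 70 days (66 to 74 with the same allowance).
- Last OLE dose to Week 18: 120 - 78 = 42 days (38 to 46).

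**Step 4: would Week 18 show an on-drug effect?** Protocol 3.2.3.3 reports that albumin in the 680 mg weekly cohort was within normal limits 3 to 4 weeks after the last dose, that is 21 to 28 days. Even the shortest interval, 38 days, is longer. The Week 18 draw would probably miss an albumin nadir reached during OLE dosing.

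**Step 5: who is affected.** Randomization is 1:1:1 with about 21 participants, so 21 / 3 = 7 are on placebo. If all enter the OLE, 7 of 21 have their whole drug exposure inside the gap.

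**The case against.** The strongest objection is that the evidence is an absent mark in a damaged copy of a table. A row with all 20 columns can still lose marks. The 8.1 drug-administration row shows five doses where the protocol gives six. The 8.2 drug-administration row shows doses under Days 3 and 38. The 8.2 chemistry row has no Week 6 or Early Withdrawal mark. The SAP's copy of the schedule is too broken to settle the matter. This stands, and it is why the first action is to check the source. Against it, the gap appears in both the chemistry and complement rows of both tables.

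Second, 3.3.1 gives no frequency and 6.9.1 no interval, so draws from baseline to Week 18 might be said to satisfy them. That is arguable as wording. It does not supply an on-drug value for a stopping rule to act on.

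Third, there are other safeguards. Vital signs, adverse events, concomitant medication, total IgG and anti-AChR continue at the OLE visits, and participants are observed for up to an hour after dosing. Investigators may order local tests, and clinically significant abnormal values must be repeated (8.4.4), although that needs a first abnormal value. Section 6.9.4, on albumin monitoring, has no text in this copy and may add draws. The complement and liver points do not depend on it.

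Fourth, the harm is likely modest. On 340 mg weekly in Phase 1, albumin stayed within normal limits, and the OLE gives that dose half as often. Protocol 3.2.3.1 reports no clinically relevant laboratory changes on drug.

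A reader might also infer more than the documents support:

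- *That 7.3 shows chemistry is expected during OLE dosing*, since it says "these labs will continue to be blinded to the investigator and study site in the OLE". The labs meant there include IgG and anti-AChR, which are drawn throughout the OLE, and the Week 18 chemistry needs blinding too.
- *That hematology was promised.* Neither 3.3.1 nor 6.9.1 names it.
- *That 8.2 plans less chemistry than 8.1 during blinded dosing.* The OLE choice comes at the end of that phase, so the two tables should agree there. The Week 6 difference is best read as a lost mark.

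**Conclusion.** The point holds for the schedule as read, with medium confidence. Table 8.2 has no chemistry or complement from Week 7 to Week 18 (77 days nominal) and none at the three OLE dosing visits. This sits badly with the 3.3.1 commitments on albumin and complement and leaves the 6.9.1 liver rules without scheduled on-drug values. The clearest consequence is for former placebo participants: up to 7 of 21, first seen 70 days after first exposure and 42 days after the last dose.

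This assumes that no marks were lost from the Week 8-16 cells, that 6.9.4 adds no albumin draws, that visits are at nominal days, and that all placebo participants enter the OLE. A reader might conclude that the sponsor left OLE participants unmonitored or exposed them to serious risk. The documents support neither: other monitoring continues, and nothing in the Phase 1 summary points to a liver or complement signal. The change is worth making because it is cheap and closes a gap in safety monitoring.

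**What to change.** 1. Check the 8.2 chemistry and complement rows against the source table. If marks at Weeks 8, 10 and 12 were lost in reading, only item 3 remains.
2. If the rows are as read, add pre-dose chemistry/hematology and complement at Weeks 8, 10 and 12. Former placebo participants would then have a first post-exposure value at Week 10, 64 - 50 = 14 days after the first dose instead of 70. Week 14 is optional; it would give a value 92 - 78 = 14 days after the third dose. Keep albumin, ALP and total protein blinded to the site, with review by the unblinded Medical Monitor.
3. In 3.3.1, cite 8.2 alongside 8.1.

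The cost is a protocol amendment and slightly more blood volume. Samples for total IgG and anti-AChR are already taken at these visits, so no new visit or venipuncture is needed. That is three extra panels per OLE participant, at most 21 x 3 = 63, or 21 x 4 = 84 with Week 14.
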